12.0 SAFETY REPORTING

For the purposes of this study, a participant is considered enrolled if they have successfully completed the screening procedure outlined above. The appointed Safety Officer provides safety oversight of the trial.

After being enrolled in the study, participant safety will be monitored regularly by the PI *and reported as needed to the Safety Officer*.

All adverse events that are both serious (SAE) and unexpected (i.e., have not been previously reported for the study's intervention), they should be reported to IRB, NIA PO and to the NIA-appointed Safety Officer (SO), within 48 hours of the study's knowledge of SAE.

The summary of all other SAEs should be reported to NIA Program Officer and to the DSMB (or a Safety Officer) quarterly (or biannually), unless otherwise requested by the DSMB or a Safety Officer.

Reports of death should be submitted to NIA Program Officer and to the Safety Officer within 24 hours of study's knowledge of death. AEs should be reported per IRB policies. They should also be reported to the NIA Program Officer and the SO, at frequency requested by NIA and/or by the SO. At minimum, annual reports are required.

Adverse Event (AE): Any unfavorable and unintended sign, symptom, or disease temporally associated with the use of a medical treatment or procedure, regardless of whether it is considered related to the medical treatment or procedure.

Serious Adverse Event (SAE): Any AE that results in any of the following outcomes:

- Death
- Life-threatening
- Event requiring inpatient hospitalization or prolongation of existing hospitalization
- Persistent or significant disability/incapacity

As this is a minimal risk psychosocial activity intervention, no AEs or SAEs are expected per NIH definitions, as none of the risks of the study will affect medical outcomes or occurrences.

- The PI will review study conduct in real time.
- The PI will review accrual, drop-outs, and protocol deviations *on an annual basis*.
- The PI will review AEs *individually in real-time, and in aggregate on an annual basis*.
- The PI will review serious SAEs *in real-time, and in aggregate on an annual basis*.
- SAEs and specific procedure-associated AEs will be reported to the Heartland IRB *when the yearly IRB report is due, unless the SAE or AE is “possibly related” or “related” to the study procedures.*

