 - *If the SAE or AE is “possibly related” or “related” to the study procedures, the SAE or AE will be reported to the IRB within 24 hours of determination of AE/SAE.*
 - If any SAEs occur, the PI will, with the assistance of the IRB, determine if any modifications need to be made to the study protocol and procedures. As this is a minimal risk study, this is highly unlikely.

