12.1 Specification of Safety Parameters

As this is a non-medical, short duration trial with no interim measures (pre-post design), there are no lab values or test scores that fill this role. If a participant becomes extremely embarrassed or agitated during an assessment or activity, they will be redirected, and their participation in the programming will stop for that session. If this occurs at a clinical level that then results in an AE, it will be reported to the IRB when the yearly IRB report is due.

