12.2 Methods and Timing for Assessing, Recording, and Analyzing Safety Parameters

The risk profile for this study is low as it is a minimal risk, nonpharmacologic intervention. As such, assessing and recording of the parameters will be done by the PI with the end goal of informing the IRB when the yearly IRB report is due. Since the PI and Experimental Team Lead will be intimately involved in all aspects of the trial, all subject data will be regularly reviewed by them and all staff will report to them on an ongoing basis.

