12.3 Reporting Procedures

SAEs and AEs are reported to the Heartland IRB when the yearly IRB report is due, unless the SAE or AE is “possibly related” or “related” to the study procedures. If the SAE or AE possibly related” or “related” to the study procedures, the SAE or AE will be reported to the IRB within 24 hours.

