12.5 Relationship To Study Intervention

All AEs will have their relationship to study participation assessed with a level of specificity appropriate to the non-pharmacological study design. The study uses the following AE attribution scale:

Not related: The AE is clearly not related to the study procedures (i.e., another cause of the event is most plausible and/or a clinically plausible temporal sequence is inconsistent with the onset of the event).

Potentially related: An event that follows a reasonable temporal sequence from the initiation of study procedures, but that could readily have been produced by a number of other factors.

Related: The AE is clearly related to the study procedures.

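### Section 12.1 routes an AE from extreme in-session distress to the yearly IRB report without the relatedness exception that 12.0 and 12.3 apply, so it gives the wrong IRB deadline whenever that AE is graded Potentially related or Related

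*Protocol*

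**What the plan says.** Protocol 12.1 covers one kind of event: extreme embarrassment or agitation arising while a participant is being assessed or is in a session. The participant is redirected and stops for that session. If the episode reaches a clinical level and "results in an AE, it will be reported to the IRB when the yearly IRB report is due". Nothing in 12.1 mentions relatedness or points to another section.

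Section 12.2 has the PI assess and record safety parameters "with the end goal of informing the IRB when the yearly IRB report is due".

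Section 12.0 sets the general rule. "SAEs and specific procedure-associated AEs will be reported to the Heartland IRB" on the yearly cycle, unless the event is possibly related or related to study procedures, in which case "the SAE or AE will be reported to the IRB within 24 hours of determination of AE/SAE". Section 12.3 repeats the yearly default and the exception: when an event is possibly related or related "to the study procedures, the SAE or AE will be reported to the IRB within 24 hours". Section 12.3 does not say when the 24 hours start.

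Section 12.0 also has a separate rule. Events that are serious and unexpected go to the IRB, the NIA Program Officer and the Safety Officer within 48 hours of the study learning of them.

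Section 12.5 has three grades: Not related, Potentially related and Related. Section 12.6 names a single expected AE tied to study procedures: extreme frustration or embarrassment during assessments or the intervention.

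**The concern.** The relatedness exception appears in the two general sections and is absent from the one sentence written for this specific event. Someone handling an episode of in-session distress would naturally turn to 12.1, because it describes that episode, and would find the yearly report as the only deadline.

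What is at stake is when the IRB hears of the event. Section 10.0 makes the post-treatment assessment the last contact with a participant. A yearly report can therefore reach the IRB after that person has finished, when it can no longer act on that person's participation. The participants have dementia, and some are enrolled on a representative's consent, so prompt independent review has value. No endpoint or analysis is affected.

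**Working it through.** The plan gives no figure to reproduce. The check compares the deadlines for the same event across sections.

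**Step 1. Deadline by grade.** Take an AE arising from extreme in-session distress. Assume that *possibly related* in 12.0 and 12.3 means *Potentially related* in 12.5, and that the 48-hour rule in 12.0 governs whenever it applies, since it carries no relatedness condition.

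| Grade under 12.5 | 12.1 | 12.0 | 12.3 |
|---|---|---|---|
| Related | Yearly | 24 hours from determination | 24 hours |
| Potentially related | Yearly | 24 hours from determination | 24 hours |
| Not related, but serious and unexpected | Yearly | 48 hours from knowledge | Yearly as worded |
| Not related, all others | Yearly | Yearly | Yearly |

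Section 12.1 agrees with both other sections only in the last row.

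**Step 2. Can the event reach the first two rows?** Section 12.5 places in the middle grade an event with a "reasonable temporal sequence from the initiation of study procedures, but that could readily have been produced by a number of other factors". Distress that arises during an assessment or session follows a study procedure in time, and the existence of other possible causes does not remove it from that grade. Section 12.6 supports this for embarrassment by listing it as procedure-linked. Agitation is not on the 12.6 list. It is one of the 12 NPI-NH symptoms (7.0), and a given episode could be graded Not related where "another cause of the event is most plausible and/or a clinically plausible temporal sequence is inconsistent with the onset of the event". So the first two rows are readily reached, but not always.

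**Step 3. What triggers the 24 hours?** Section 12.0 applies its yearly default to procedure-associated AEs as well. Being listed in 12.6 therefore does not by itself start the 24-hour clock. The relatedness grade does.

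**Step 4. Size of the gap.** For a Potentially related or Related AE, the choice is 24 hours or the next yearly report, up to about 12 months. Section 1.0 gives a 4-week baseline and an 8-week intervention: 4 + 8 = 12 weeks per participant, against a 52-week reporting cycle. The date of the yearly report is not given, so the actual delay could be anything from almost none to about 12 months, and no probability can be attached to it.

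**Step 5. Terminology.** *Possibly related* appears twice in 12.0 and twice in 12.3 (2 + 2 = 4) and is not a grade on the 12.5 scale.

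**The case against.** The sections can be read together. Section 12.3 is the reporting-procedures section and its exception covers any AE or SAE. Section 12.1 does not disapply it, so 12.1 could be taken as the shared default stated without its qualifier. That reading is available, but 12.1 does not state it, and a rule for a specific event is easily taken to displace a general one. If 12.3 does override, the 12.1 sentence is right only for some events graded Not related. The wording needs repair either way.

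Other objections limit the point, and they stand:

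- A reader might infer that 12.1 gives the wrong deadline in most cases. The documents give no grading frequency, and the Not related grade is open to some agitation.
- A reader might infer that all outside review is delayed. Only the IRB route is shown to be affected. Under 12.0, AEs also go to the NIA Program Officer and the Safety Officer at the frequency they request, and AEs are to follow IRB policies, which are not included. Section 17.0 refers to a separate monitoring plan. None of these shows a fixed short deadline that would correct 12.1, and neither do the as-needed Safety Reports in 17.1.
- A reader might infer that participants are left unprotected. Immediate protection does not depend on IRB timing: the session or assessment stops (12.1, 12.6), the PI reviews AEs "individually in real-time, and in aggregate on an annual basis", and AE reporting is on the weekly agenda (16.3). A late report would require the PI or Experimental Team Leader to apply 12.1 and overlook 12.0 and 12.3.
- The two relatedness terms are near-synonyms with only one plausible match, and 12.2 states a goal, not a deadline. Both are minor.

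**Conclusion.** The inconsistency is real. For an AE from extreme in-session distress graded Potentially related or Related, 12.1 as written gives the yearly IRB report where 12.0 and 12.3 require 24 hours. The conclusion assumes that *possibly related* was meant to match *Potentially related*.

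The consequence is limited to the timing of the IRB report, and mainly to AEs that are not both serious and unexpected. How often the deadlines would clash is unknown. The study is described as minimal risk and expects 12 completers. The point is still worth correcting, because it concerns a safety deadline for a kind of event the protocol itself anticipates, and the correction is cheap.

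**What to change.** 1. Replace the last sentence of 12.1 with wording such as:

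> If this leads to an AE, it is graded under 12.5. An AE graded Potentially related or Related goes to the IRB no later than 24 hours after determination (12.0, 12.3). One that is serious and unexpected goes within 48 hours of the study's knowledge (12.0). Where both apply, the earlier deadline holds. Any other AE goes in the yearly IRB report.

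   The 48-hour clause is needed: sending every Not related event to the yearly report would contradict 12.0.

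2. In 12.2, replace the reference to the yearly report with a pointer to the timelines in 12.0 and 12.3.

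3. As minor tidying, change *possibly related* to *Potentially related* in the four places in 12.0 and 12.3, to match the 12.5 scale.

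The cost is wording in four subsections (12.0 to 12.3). It needs no new data, visits or analyses.

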12.2 Methods and Timing for Assessing, Recording, and Analyzing Safety Parameters

The risk profile for this study is low as it is a minimal risk, nonpharmacologic intervention. As such, assessing and recording of the parameters will be done by the PI with the end goal of informing the IRB when the yearly IRB report is due. Since the PI and Experimental Team Lead will be intimately involved in all aspects of the trial, all subject data will be regularly reviewed by them and all staff will report to them on an ongoing basis.

12.3 Reporting Procedures

SAEs and AEs are reported to the Heartland IRB when the yearly IRB report is due, unless the SAE or AE is “possibly related” or “related” to the study procedures. If the SAE or AE possibly related” or “related” to the study procedures, the SAE or AE will be reported to the IRB within 24 hours.

12.4 Severity of Event

AEs will be graded according to the following scale:

Mild: An experience that is transient and requires no special treatment or intervention.

The experience does not generally interfere with usual daily activities. This includes transient laboratory test alterations.

Moderate: An experience that is alleviated with simple therapeutic treatments. The experience impacts usual daily activities. Includes laboratory test alterations indicating injury, but without long-term risk.

Severe: An experience that requires therapeutic intervention. The experience interrupts usual daily activities. If hospitalization (or prolongation of hospitalization) is required for treatment it becomes an SAE.

12.5 Relationship To Study Intervention

All AEs will have their relationship to study participation assessed with a level of specificity appropriate to the non-pharmacological study design. The study uses the following AE attribution scale:

Not related: The AE is clearly not related to the study procedures (i.e., another cause of the event is most plausible and/or a clinically plausible temporal sequence is inconsistent with the onset of the event).

Potentially related: An event that follows a reasonable temporal sequence from the initiation of study procedures, but that could readily have been produced by a number of other factors.

Related: The AE is clearly related to the study procedures.

12.6 Follow-up for Adverse Events

Expected AEs

Expected AEs associated with the study procedures include:

- Extreme Feelings of Frustration/Embarrassment during the Assessments / Intervention

AE Management

- Only staff with proper experience in working with vulnerable populations will be permitted to take part in primary data collection. This will increase the chances that they know how to reduce such feelings in participants
- All SPs will receive training on how to recognize signs of frustration and embarrassment and what to do in such situations.
- SPs will be instructed that, if such signs are present, the assessment or activity will be discontinued and/or the participant will be given an alternative activity.

12.7 Unanticipated Problems

Upon notification of an Unanticipated Problem, the Experimental Team Leader or PI will notify all appropriate parties as described in the protocol:

1. The Experimental Team Leader will immediately notify the PI.
2. The PI will send a notification email to the IRB.
3. The PI will advise the Study Team regarding screening, enrollment, and ongoing participation.
4. Upon advisement by the IRB, the PI will determine the study's status and notify the Study Team.

13.0 STUDY COMPLIANCE

The PI will maintain a Protocol Deviation / Violation Log, in which he will report of all protocol deviations/violations, including but not limited to the following:

- Enrollment of an ineligible participant
- Failure to obtain Informed Consent
- Failure to keep IRB approval up-to-date
- Wrong treatment administered to participant
- Follow-up visit at a time point different from that specified in the protocol

14.0 DATA COLLECTION AND STUDY FORMS

The following documents are used in this study. Descriptions of measures are included above.

PWD

Screening Documents

1. PWD Initial Screening / Inclusion Form

Baseline Assessments / Observations Documents

1. Chart Review Form
2. SPMSQ
3. DEMQOL
4. GDS-SF
5. ULS
6. NPI-NH

Intervention Period Data Collection

1. Satisfaction Question Form
2. MPES

Post-Treatment Assessment Documents

1. DEMQOL
2. GDS-SF
3. ULS
4. NPI-NH

15.1 Source Documentation

This section describes how participant data are maintained in the study.

Definitions: A source document is any document on which study data are initially recorded. Source documents for this study include demographics forms, medical records, standardized test forms, satisfaction questionnaires, and engagement forms, etc. Most source documents are electronic in nature and will also serve as electronic Case Report Forms (eCRFs) to document study-specific data requirements. This method reduces the likelihood of transcription errors. All data will be checked and cleaned during a QA process to ensure data integrity.

All essential study documents will be retained by the investigator in an electronic Participant Binder and include:

- Source documents
- Measures administered to the participant
- Measures administered to the proxy interviews
- eCRFs
- Applicable *Notes to File* (including *Notes to File* that indicate errors in forms)

Note: The only exception to this is that Resident Consent Documents are kept in an electronic folder named “Participants and Consents.” This keeps the participant name separate from de-identified data.

At the conclusion of the study, all source documents, eCRFs, and other required documentation will be kept with study records as required by protocol and IRB guidelines.

Please note: all MPES observations will be conducted via a HIPAA compliant Google Form. Submitted responses will automatically be sent to a database. As such, there will be no need to save a corresponding PDF file in each participant's digital binder for each MPES observation. To prevent changing of data in the database, there will be a lock on the database preventing changing of data, except by the PI or Experimental Team Leader. Although each MPES observation will not have a corresponding PDF file in the participant's digital binder, a PDF will be generated for each observation for auditing purposes. The PDFs will be placed in a single folder. MPES observations will be spot checked for accuracy by comparing database data to PDF form data.

15.2 Forms Maintenance

All forms will be stored in electronic participant “binders.” Forms which are collected digitally will automatically be saved to a secure, HIPAA-compliant database and then manually distributed to the correct participant binder. Hard copy forms will be scanned and placed into the proper digital binder.

Please note: all MPES observations will be conducted via a HIPAA compliant Google Form. Submitted responses will automatically be sent to a database. As such, there will be no need to save a

corresponding PDF file in each participant's digital binder for each MPES observation. To prevent changing of data in the database, there will be a lock on the database preventing changing of data, except by the PI or Experimental Team Leader. Although each MPES observation will not have a corresponding PDF file in the participant's digital binder, a PDF will be generated for each observation for auditing purposes. The PDFs will be placed in a single folder. MPES observations will be spot checked for accuracy by comparing database data to PDF form data.

15.3 General Instructions for Completing Forms

For All forms:

- All forms should be filled out electronically.
- Any hard-copy forms will be scanned as soon as feasible and become the source document.
- Completed forms should be saved in the participant's digital binder (file folder with their ID number)
- To ensure the best possible level of confidentiality, after scanning hard copy forms, these forms will be stored in a secure area. After data from hard copy forms have been entered / double checked, such forms will be shredded.
- The Experimental Team Leader and/or PI will spot check a subset of forms before they are entered into SPSS to ensure that proper protocols are being adhered to and data is appropriately cleaned.
- After data on digital forms are confirmed to be accurate, researchers will flatten the digital form (to prevent accidental changes to the file) and save it to the participant's digital binder.
 - The file name will have descriptive details about what is included in the file (e.g., Resident Assessment, HBC Session Observation / Evaluation Form, etc.)
 - In addition, the researcher will end the file name with his/her initials and the date (e.g., dw_2022_01_01)
- The Experimental Team Leader is responsible for updating forms, as needed.
- The PI will review and approve all changes to forms.
- During weekly meeting, issues with data collection, including possible problems with forms should be discussed by study team members.
- Researchers should be sure to completely fill out all forms.
- Participants must not be identified by name on any study document submitted with the forms. If research sites provide forms with the participants name on them, researchers will redact the participant's name and replace with his/her identification (ID) number.
- Researchers should complete the header information on EVERY page, including pages for which no study data are recorded.
- The participant ID must be recorded on EVERY page, including pages for which no study data are recorded.
- Time: Use a 24-hour clock (e.g., 14:00 to indicate 2:00 p.m.) unless otherwise specified.
- All dates must be verifiable by source documents. Historical dates are sometimes not known (e.g., date of first symptom); therefore, conventions for missing days and/or months should be described (e.g., UNK or 99).
- Use of abbreviations not specifically noted in the instructions for completing the forms can be problematic and should be held to a minimum.

- Comments written extraneously on forms cannot be captured in the database; thus, write only in the spaces indicated.
- If an error has been made on the study forms, place a single line through the erroneous entry and record the date and your initials. Indicate the correct response.
- Do not skip any items. Some items may carry "Unknown" or "Not Applicable" response choices which should be checked when necessary.
- Data may not be available to complete the form for various reasons. Circle the item for which data is not available and indicate the reason near the appropriate field:
- If an evaluation was not done, write ND and provide a reason.
- If the information is not available, but the evaluation was done, write NAV.
 - Only in rare circumstances, as in the case of lost documentation, should NAV be recorded on the form. Every effort should be made to obtain the information requested.
- If an evaluation is not applicable, write NA.
- Incomplete or Illegible forms: Incomplete forms that do not have adequate explanation (as described above) compromise the integrity of the entire study.
- If/when site-staff share a document with a participant's name on it, the name of the person will be digitally redacted, and the ID number of the person put in place of the name
 - To preserve privacy, the document with the name of the person will be deleted
 - The version with the ID number will be placed in the appropriate digital file folder.

For Digital Forms:

When a form is completed, it should be placed in the digital binder (file folder) for the individual participant.

For Hard Copy Forms:

Hard copy forms should only be used when a tablet and/or internet is unavailable. If used, hard copy forms must be scanned immediately after collection and uploaded to the participant binder. The scanned version will then be considered the source document. Hard copy will then be stored in a secured area. When completing hard copy study forms, print using dark ink.

